4.3.2. Handling of Subject Withdrawals or Terminations

If a subject is withdrawn or discontinued from the study, the reason for withdrawal from the study is to be recorded in the source documents and on the eCRF. All subjects withdrawn prior to completing 12 months of study drug treatment should be encouraged to complete study procedures scheduled for the Month 12/End of Treatment (EOT) visit as soon as possible, and to return in 1 month for a Follow-up visit (EOS Visit). All AEs should be followed as described in Section 7. Subjects who discontinue prematurely or are withdrawn from the study will not be replaced. For early terminations that occur on or after the day of study drug initiation, every effort should be made to document the subject's outcome, regardless of cause. Whenever a subject is discontinued prematurely, the Sponsor's Medical Monitor must be notified.

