### **1.2. Study Design**

#### **1.2.1. Synopsis of Study Design**

This is a randomized, open-label, non-inferiority, multicenter study of abaloparatide-sMTS compared with abaloparatide-SC for the treatment of postmenopausal women with osteoporosis.

[figure not shown]
The study will consist of a Screening Period (up to 2 months), a Pretreatment Period (1 week), and a Treatment Period (12 months) with a final visit 1 month after the last dose of study drug (Follow-Up/End of Study [EOS] visit). 1 month is defined as 30 days in this study. Thus, subjects will participate in the study for up to 16 months.

Eligible subjects will be randomized in a 1:1 treatment ratio to either abaloparatide-sMTS or abaloparatide-SC using a permuted block randomization scheme. During the Treatment Period, subjects will self-administer study drug once a day for 12 months and visit the study site on Days 1 and 14 and Months 1, 2, 3, 4, 5, 6, 7, 8, 9, 10, 11, 12 and Month 13 for the follow-up visit.

All subjects will be provided calcium and Vitamin D to ensure that their daily intake is 1200 mg/day and 800 IU/day, respectively, or a dose determined by the investigator and agreed by the Sponsor Medical Monitor according to the subject's need.

The study design is presented in [Figure 1](#).

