### **3. GENERAL STATISTICAL METHODS**

#### **3.1. Sample Size Planned and Specified in the Protocol**

The previous pivotal, Phase 3, multicenter, randomized, open-label active- and double-blind placebo-controlled study of abaloparatide-SC (Study BA058-05-003) showed that the placebo-adjusted effect of abaloparatide-SC 80 µg on the percent change from baseline in lumbar spine BMD based on a Mixed-Effect Model Repeated Measures (MMRM) analysis was 9.096% (95% CI: 8.557%, 9.634%) at 12 months. According to FDA's *Guidance for Industry: Non-Inferiority Clinical Trials to Establish Effectiveness* (FDA, 2016), the lower bound of this confidence interval (CI) can be considered as the historical treatment effect of abaloparatide-SC versus placebo,  $M_1$  (=8.557%). Based on FDA's recommendation of a clinically meaningful difference of 2.0% between treatment groups, a non-inferiority (NI) margin,  $M_2$ , is selected at 2.0% to preserve approximately 77% of  $M_1$ , the historical treatment effect of abaloparatide-SC.

This preserved effect supports the superiority to placebo because the amount of preserved effect, 6.557% (=77%  $\times M_1$ ) is larger than the placebo-adjusted effect of alendronate 10 mg daily (5.4%; Fosamax® USPI) and of denosumab 60 mg once every 6 months (5.5%; Bolognese et al, 2013) on lumbar spine BMD at 12 months. Furthermore, the placebo-adjusted effect of teriparatide observed in the previous Phase 3 study (Study BA058-05-003) based on an MMRM analysis was 7.841% (95% CI: 7.384%, 8.297%). Thus, the proposed NI margin will preserve 89% (=6.557/7.384) of the effect of teriparatide, another market-approved anabolic agent.

Non-inferiority of abaloparatide-sMTS to abaloparatide-SC will be concluded if the lower bound of the two-sided 95% CI for the estimated treatment difference (abaloparatide-sMTS minus abaloparatide-SC) in the percent change from baseline in lumbar spine BMD at 12 months is above -2.0%, using an MMRM analysis.

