A sample size of 426 subjects will provide at least 90% power to conclude the non-inferiority of abaloparatide-sMTS 300 µg to abaloparatide-SC 80 µg, assuming a true mean difference of 0% and a standard deviation of 6.35%. To ensure an analysis size of 426 subjects, an overall sample size of 474 subjects (237 subjects per group) will be randomized, anticipating that approximately 10% of treated subjects may not have both a baseline lumbar spine BMD measurement and at least one post-baseline lumbar spine BMD measurement.

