#### **3.2. General Methods**

Summary tables will be presented by treatment group (abaloparatide-sMTS and abaloparatide-SC) and overall, when appropriate. For categorical data, summary tabulations of the number and percentage of subjects within each category of the parameter will be presented. When tabulating categorical data, "missing" will be included as a category and the number of subjects with missing data will be presented. For continuous data, the number of subjects, mean, standard deviation (SD), median, minimum, interquartile range (Q1 and Q3), and maximum will be presented.

All data listings that contain an evaluation date will contain a relative study day. Screening, pretreatment, and on-treatment study days will be numbered relative to the day of the first dose of study drug which is designated as Day 1. Study days prior to the first dose of study drug will be calculated as: [date of assessment – date of first dose of study drug]. Study days on or after

the first dose of study drug will be calculated as: [date of assessment – date of first dose of study drug + 1].

Unless otherwise specified, all statistical tests will be two-sided with a significance level of 5%.

Where applicable, CIs about a parameter estimate will be presented using the same number of decimal places as the parameter estimate, and p-values will be rounded to 4 decimal places prior to assessment of statistical significance.

The anti-drug antibody assessment in the serum samples for immunogenicity testing will be analyzed and reported separately. All the planned efficacy and safety analyses related to immunogenicity results and antibody status will also be reported separately.

This study is being conducted during the COVID-19 pandemic. The COVID-19 outbreak emerged in December 2019 and quickly became a global pandemic as declared by the World Health Organization in early March 2020. At that time, a variety of mitigations to assure safety of participants and address operational issues were implemented by RADIUS. To investigate the effect of the COVID-19 pandemic on study conduct, additional analyses will be conducted as described in the efficacy and safety analysis sections.

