#### **4.4. Efficacy Analyses**

The mITT population will be the primary population for the analysis of all efficacy endpoints. All efficacy endpoints will also be analyzed with the ITT and PP populations. Subjects will be analyzed according to their randomized treatment group.

All BMD-related endpoints will be derived from the Calyx-corrected BMD measurements.

BMD scans may be deemed unevaluable at the first reading and a repeat BMD scan may be performed. The re-scan BMD assessment will be recorded as an unscheduled visit for the corresponding nominal visit. To determine the assessment that will be used for a given study visit by the analysis window convention, all BMD assessments (including unscheduled BMD assessments) will be considered. In the efficacy analyses by nominal visit, unscheduled BMD assessments will be used if the BMD assessment at the nominal visit is not available but an unscheduled BMD assessment for the same nominal visit is available.

Analyses of the BMD-related efficacy endpoints and the serum markers of bone metabolism (s-PINP and s-CTX) will be conducted using the analysis visit windows defined in [Table 3](#) of [Section 3.12](#) as the primary analysis. Analyses of the BMD-related efficacy endpoints and the serum markers of bone metabolism (s-PINP and s-CTX) using the nominal visits will also be presented as supportive analyses. Study sites collected samples for bone turnover marker assessment in 4 aliquots per subject at each collection timepoint. When more than 1 aliquot was analyzed for a given timepoint for a subject, the average of the results for that timepoint for that subject will be used in the analysis.

Unless otherwise specified, all CIs, statistical tests, and p-values will be reported as nominal 2-sided from testing for treatment difference, with a significance level of 0.05.

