4. 100 datasets will be generated and will be analyzed using an ANCOVA model with treatment and DXA instrument manufacturer as fixed effects, and the baseline lumbar spine BMD as a covariate for the comparison of percent change of BMD from baseline to Month 12.

5. Treatment effects (difference in LS means between treatments) from these 100 analyses will then be combined using Rubin's Method via SAS PROC MIANALYZE procedure for overall statistical inference.

As a supportive analysis, the primary efficacy endpoint will be analyzed using an ANCOVA model using the last observation carried forward (LOCF) method. The ANCOVA model will include treatment and DXA instrument manufacturer as fixed effects, and baseline lumbar spine BMD as covariate. The LS mean and corresponding 95% CI for the difference between treatment groups (abaloparatide-sMTS minus abaloparatide-SC) at Month 12 will be presented. Missing data imputation based on the LOCF method will be performed as follows:

- a. If baseline BMD is missing, no imputation for post-baseline value will be done and this subject's data will be excluded from the analysis.
- b. If baseline BMD is observed, missing post-baseline BMD will be imputed by the last observed value prior to the missing assessment. That is, if a value is missing at a post-baseline time point, the post-baseline BMD will be imputed using the last value observed at any time (could be a value obtained at an unscheduled visit) between baseline (inclusive) and the specified post-baseline time point.

To investigate the effect of the COVID-19 pandemic, the following sensitivity analyses will also be performed:

- a. MMRM analysis using the nominal visit
- b. MMRM analysis excluding BMD measurements collected outside the allowable time period for data collection. In this analysis, BMD assessments are allocated to a Visit based on the inclusion rules shown in [Table 4](#) below for Sensitivity Analysis b).
- c. MMRM analysis excluding BMD measurements which are more than 30 days after the ideal visit date. In this analysis, BMD assessments are allocated to a Visit based on the inclusion rules shown in [Table 4](#) below for Sensitivity Analysis c).

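### In the supportive nominal-visit analyses, an early-termination EOT scan or sample can count as a Month 12 value; the bias can go either way and the primary analysis is untouched.

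*SAP*

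**What the plan says.** Protocol 4.3.2 encourages subjects withdrawn before 12 months to complete the "study procedures scheduled for the Month 12/End of Treatment (EOT) visit as soon as possible". Protocol 6.7 says much the same for women who no longer wish to take part. Month 12 and EOT are one visit, Visit 16, in the schedule and in Protocol 6.2.7.14. That visit includes DXA, s-PINP and s-CTX. The schedule has no separate early-termination visit.

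SAP 4.4 bases the primary analyses of BMD and the markers on the study-day windows of Table 3, where Month 12 means Day 301 or later. It adds that analyses "using the nominal visits will also be presented as supportive analyses". SAP 4.4.1.2 then lists, as analysis a of its pandemic set, an "MMRM analysis using the nominal visit". Analyses b and c of that set have day ranges in Table 4. SAP 4.4.2 repeats the pandemic set for total hip and femoral neck, and SAP 4.4.4 repeats the marker analysis on nominal visits.

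The only allocation rule for nominal-visit BMD (SAP 4.4) concerns when an unscheduled re-scan may stand in for a missing scheduled one. Nothing moves or excludes an early EOT assessment.

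**The concern.** Followed as written, the nominal-visit rule scores a scan by its visit label. A woman who leaves in Month 5 and attends promptly has a scan at about Day 150 labelled Month 12/EOT. Her scan reflects about five months of treatment but enters the model as a 12-month response.

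Analysis a is meant to show whether the pandemic-related visit windows matter. If early EOT scans are mixed into its Month 12 column, it can agree or disagree with the primary result for a reason unrelated to the pandemic, and the reader cannot tell which. In a non-inferiority comparison, the size and sign of such a bias also matter for how far the analysis can be taken as support.

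**Working it through.** **Where one scan goes.** Take a Month 12/EOT scan at Day 150:

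| Analysis | Month 12 range (days) | Where the scan goes |
|---|---|---|
| Primary (Table 3) | 301 or later | Month 6 window (121–300) |
| Sensitivity b (Table 4) | 356–364 | Month 6 window (121–300) |
| Sensitivity c (Table 4) | 301–390 | Month 6 window (121–210) |
| Sensitivity a and supportive nominal-visit | none stated | Month 12 |

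**The plan's own figure.** SAP 3.1: "A sample size of 426 subjects will provide at least 90% power to conclude the non-inferiority", "assuming a true mean difference of 0% and a standard deviation of 6.35" percent. The margin is 2.0 points ("a non-inferiority (NI) margin, $M_2$ , is selected at 2.0" percent). Allocation is equal ("Eligible subjects will be randomized in a 1:1 treatment ratio"). SAP 3.2 sets the level: "all statistical tests will be two-sided with a significance level of 5" percent, so 0.025 one-sided for the lower bound.
- Normal approximation: n per arm = 2 × (6.35/2.0)² × (1.960 + 1.282)² ≈ 212.
- Noncentral t: power is 0.8989 at 212 and 0.9003 at 213 per arm, so 426 in total, as stated.
- 426/0.9 = 473.3, rounded up to 474. The plan's figures are reproduced.

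**Model for mislabelled scans.**
- gC = 9.096, the 12-month SC effect in SAP 3.1. It is placebo-adjusted; using it as the SC gain is an assumption.
- gT = gC + true difference.
- dT, dC = share of the sMTS and SC arms with an early EOT scan counted as Month 12. Not in the documents; 5–15% assumed.
- f = fraction of the 12-month gain reached at that scan. Not in the documents; 0.4–0.8 assumed.
- Estimate = gT[1 − dT(1 − f)] − gC[1 − dC(1 − f)], so shift = (1 − f)(gC·dC − gT·dT).
- SE = 6.35 × √(2/213) = 0.615.
- P = Φ((estimate + 2)/SE − 1.96), the chance that the nominal-visit lower bound clears -2.0. It is 2.5% at a true difference of -2 with no mislabelling.

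**Results at a true difference of -2 (gT = 7.096).**
- Equal shares: shift = (1 − f) × d × 2.0. Smallest: 0.2 × 0.05 × 2.0 = +0.02 (P 2.7%). Middle (10%, f = 0.6): 0.4 × 0.10 × 2.0 = +0.08 (P 3.4%). Largest: 0.6 × 0.15 × 2.0 = +0.18 (P 4.8%).
- 15% sMTS, 5% SC: (1 − f)(0.4548 − 1.0644) = -0.12 to -0.37. P falls to 1.6–0.5%.
- 5% sMTS, 15% SC: (1 − f)(1.3644 − 0.3548) = +0.20 to +0.61. P rises to 5.1–16.5%.
- Sign change: shift is zero when dT/dC = 9.096/7.096 = 1.28.

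**Results at a true difference of 0.**
- Equal shares: no shift.
- 15% sMTS, 5% SC: -(1 − f) × 9.096 × 0.10 = -0.18 to -0.55. The chance of clearing the margin falls from 90% to 84–66%.

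**Cross-check by simulation**, with an assumed covariance (Month 12 SD 6.35) and a true difference of -2. Nominal-visit bias was +0.06 at 10%/10%, -0.20 at 15% sMTS/5% SC and +0.36 at 5% sMTS/15% SC. A likelihood analysis that allocated scans by study day had bias between -0.01 and +0.05 over all scenarios run. Its P at a true difference of -2 was 1.8–3.0%, consistent with 2.5% within simulation error.

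No size is worked out for the markers, because the documents give no marker trajectory. The labelling problem is the same.

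**The case against.** The strongest reply is that nothing decisive rests on these analyses. They are supportive; analyses b and c are restricted by date; and the tipping-point, washout and LOCF analyses deal separately with missing data. That is right, and it limits the consequence. It does not make analysis a a sound check.

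A reader might infer that the error always pulls the arms together and so favours non-inferiority. The documents do not support this. It requires sMTS to be truly worse, with early-EOT shares similar or higher on SC, and no document gives the split by arm. Above a ratio of 1.28 at a true difference of -2, the bias goes the other way.

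The number of such scans may also be small. Early leavers are only encouraged to attend, and the 10% allowance in SAP 3.1 covers women without a baseline and at least one post-baseline scan, which is a different quantity. This stands: the shares used here are assumptions.

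Finally, the database might label early-termination visits separately. SAP 4.3.1 does mention an early termination visit date, but only for imputing the last dose date. Neither document says that such a visit has its own nominal label.

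**Conclusion.** The gap is real and confined to the nominal-visit efficacy analyses of BMD, s-PINP and s-CTX. As written, an early EOT assessment can enter as a 12-month value. The resulting bias in the Month 12 BMD difference has no fixed sign. With equal shares of 5–15% and 40–80% of the gain reached, it is 0.02–0.18 points toward non-inferiority at a true difference of -2, and zero at no true difference. With shares of 5% and 15% in opposite arms, it reaches about 0.4 points against or 0.6 points in favour at a true difference of -2. These figures rest on assumed shares and fractions, on 9.096 standing for the SC gain, and on a simple mean model with the planned SE.

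A reader might also infer that the trial's type I error is inflated. It is not. SAP 4.4 bases the primary analysis on Table 3, where a scan before Day 301 cannot be a Month 12 value. The P values above describe only how the supportive analysis would read. This is a worthwhile correction to a robustness check.

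**What to change.** In SAP 4.4, state that for nominal-visit efficacy analyses (BMD, s-PINP and s-CTX only) a Month 12/EOT assessment before study day 301 is not a Month 12 value. Allocate it by the Table 3 windows if that visit has no value; otherwise leave it out. Report the number and study day of such assessments by arm.

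Table 3 is preferable to a nearest-visit rule, which would conflict with it: a Day 125 scan is nearest Month 3, but Table 3 places it in Month 6.

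Leave the by-visit safety tables unchanged. ECG and coagulation have few scheduled visits, so a day rule there would tend to drop early EOT safety data.

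The cost is a short addition to the text and to the programming, with no new data. A few values leave the nominal Month 12 column, and the primary analysis does not change.

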**Table 4: Visit Windows for DXA Assessments for Sensitivity Analyses.**

Visit	Ideal Visit Day	Sensitivity Analysis b): Allowable days from first dose of study drug	Sensitivity Analysis c): Allowable days from first dose of study drug
Month 3	90	2- 120 days	2 - 120 days
Month 6	180	121 - 300 days	121 - 210 days
Month 12	360	356 - 364 days	301 – 390 days

If there is more than 1 assessment for a parameter within the same visit window, the assessment with the date closest to the ideal visit day will be used. In the event that 2 assessments are equidistant to the ideal visit day, the later of the assessments will be used.

#### **4.4.1.3. Subgroup Analysis**

Subgroup analyses for each of the subgroups defined in [Section 3.8](#) will be performed on the primary efficacy endpoint using MMRM analysis for mITT, ITT, and PP populations. The LS means and corresponding 95% CIs for the treatment differences (abaloparatide-sMTS minus

abaloparatide-SC) at Month 12 for each subgroup will be derived. A forest plot of the estimated treatment difference (and the corresponding 95% CI) will be presented for each subgroup. Additional exploratory analyses examining subgroup effect and treatment by subgroup interaction may be performed, if warranted.

#### **4.4.1.4. Analysis by Anti-Abaloparatide Antibody Status**

The analysis of the primary efficacy endpoint using MMRM model will also be repeated for the Antibody population within each treatment group, in which the subjects who are ADA+ at any post-baseline time point will be compared with subjects who are ADA- at all post-baseline time points. The MMRM model will include the fixed effects of ADA status, DXA instrument manufacturer, visit, and ADA status-by-visit interaction, with the baseline lumbar spine BMD as covariate.

#### **4.4.2. Secondary Efficacy Endpoints**

The secondary efficacy endpoints are:

- Percent change from baseline in total hip BMD at 12 months
- Percent change from baseline in femoral neck BMD at 12 months

The secondary efficacy endpoints will be analyzed using the MMRM model similar to the analysis for the primary efficacy endpoint, with the appropriate baseline BMD as covariate for the mITT, ITT, and PP populations. The LS means of the secondary efficacy endpoints for the treatment groups and the treatment differences will be estimated. The corresponding 95% CIs will be presented.

The sensitivity analyses using washout imputation using the observed baseline values described in [Section 4.4.1.2](#) will also be applied to these 2 endpoints.

In addition, sensitivity analyses for addressing the effect of the COVID-19 pandemic and supportive analyses using ANCOVA model with LOCF imputation method, as with the analyses for the primary efficacy endpoint, will also be conducted with the appropriate baseline BMD as covariate. Subgroup analyses using the MMRM model will be performed on the secondary efficacy endpoints using mITT, ITT and PP populations for each of the subgroups defined in [Section 3.8](#). The analyses will use MMRM analysis models as described above. A forest plot of the estimated LS mean (and the corresponding 95% CI) of the difference between the treatment groups will be presented by subgroup for each of the secondary efficacy endpoints.

The analysis of the secondary efficacy endpoints using MMRM model will also be repeated for the Antibody population within each treatment group, in which the subjects who are ADA+ at any post-baseline time point will be compared with subjects who are ADA- at all post-baseline time points, with fixed effects of ADA status (ADA+ vs. ADA-), DXA instrument manufacturer, visit, and ADA status-by-visit, and with the appropriate baseline BMD as a covariate.

#### **4.4.3. Additional Efficacy Endpoints**

Additional efficacy endpoints are:

- Percent change from baseline in
  - Lumbar spine BMD at 3 and 6 months

- Total hip BMD at 3 and 6 months
- Femoral neck BMD at 3 and 6 months

Additional efficacy endpoints will be analyzed using the MMRM model similar to the analysis for the primary efficacy endpoint for the mITT and PP populations, with the appropriate baseline BMD as covariate. The LS means of additional efficacy endpoints for the treatment groups and the treatment differences will be estimated. The corresponding 95% CIs will be provided.

Percent (%) changes from baseline in BMD will be summarized using descriptive statistics by visit (Month 3, 6, and 12) for each treatment group for the mITT and PP populations.

Plots will be presented for the LS mean ( $\pm$  SE) estimated from MMRM models of the percent change in BMD of the lumbar spine, total hip, and femoral neck over the 12-month treatment period for each of the treatment groups.

